8.4.3.2 Expectedness

IMM will be responsible for determining whether an adverse event (AE) is expected or unexpected. An AE will be considered unexpected if the nature, severity, or frequency of the event is not consistent with the risk information previously described for the study intervention.

8.4.4 Time Period and Frequency for Event Assessment and Follow-Up

The occurrence of an adverse event (AE) or serious adverse event (SAE) may come to the attention of study personnel during study visits and interviews of a study participant presenting for medical care, or upon review by a study monitor.

Abbreviated Title: Tolerability and efficacy of ketogenic diet in Parkinson's Disease

Version Date: 04/19/2021

All AEs including local and systemic reactions not meeting the criteria for SAEs will be captured on the appropriate case report form (CRF). Information to be collected includes event description, time of onset, clinician's assessment of severity, relationship to study product (assessed only by those with the training and authority to make a diagnosis), and time of resolution/stabilization of the event. All AEs occurring while on study must be documented appropriately regardless of relationship. All AEs will be followed to adequate resolution.

AE will be solicited through daily keto-induction symptom worksheets. Opportunity for unsolicited AE will be provided / encouraged, with instructions for conversation to occur initially with study PI / IMM to maintain blinding of study raters, when AE is not serious and is non-emergent.

Any medical condition that is present at the time that the participant is screened will be considered as baseline and not reported as an AE. However, if the study participant's condition deteriorates at any time during the study, it will be recorded as an AE.

Changes in the severity of an AE will be documented to allow an assessment of the duration of the event at each level of severity to be performed. AEs characterized as intermittent require documentation of onset and duration of each episode.

Study PI will communicate to IMM and record all reportable events with start dates occurring any time after informed consent is obtained until 7 (for non-serious AEs) or 30 days (for SAEs) after the last day of study participation. Study AI will also be involved in evaluation after study completion when non-emergent. Events will be followed for outcome information until resolution or stabilization.

8.4.5 Adverse Event Reporting

Reportable events will be tracked and reported in compliance with Policy 801.

8.4.6 Serious Adverse Event Reporting

The study investigator will immediately report to the IRB any serious adverse event, whether or not considered study intervention related, including those listed in the protocol and must include an assessment of whether there is a reasonable possibility that the study intervention caused the event. Study endpoints that are serious adverse events (e.g., all-cause mortality) must be reported in accordance with the protocol unless there is evidence suggesting a causal relationship between the study intervention and the event (e.g., death from anaphylaxis). In that case, the investigator must immediately report the event to the IRB.

All serious adverse events (SAEs) will be followed until satisfactory resolution or until the site investigator deems the event to be chronic or the participant is stable. Other supporting documentation of the event may be requested by the Data Coordinating Center (DCC) and should be provided as soon as possible.

The Principal Investigator (PI) will be responsible for notifying the Food and Drug Administration (FDA) of any unexpected fatal or life-threatening suspected adverse reaction as soon as possible, but in no case later than 7 calendar days after the PI's initial receipt of the information. In addition, the sponsor must notify FDA and all participating investigators in an Investigational New Drug (IND) safety report of potential serious risks, from clinical trials or any other source, as soon as possible, but in no case later than 15 calendar days after the PI determines that the information qualifies for reporting.

Reportable events will be tracked and reported in compliance with Policy 801.

Abbreviated Title: Tolerability and efficacy of ketogenic diet in Parkinson’s Disease

Version Date: 04/19/2021

8.4.7 Events of Special Interest - N/A

8.4.8 Reporting of Pregnancy - N/A

8.5 UNANTICIPATED PROBLEMS

8.5.1 Definition of Unanticipated Problems (UP)

Any incident, experience, or outcome that meets **all** of the following criteria:

- Unexpected in terms of nature, severity, or frequency given (a) the research procedures that are described in the protocol-related documents, such as the Institutional Review Board (IRB)-approved research protocol and informed consent document; and (b) the characteristics of the participant population being studied; and
- Related or possibly related to participation in the research (“possibly related” means there is a reasonable possibility that the incident, experience, or outcome may have been caused by the procedures involved in the research); and
- Suggests that the research places participants or others (which many include research staff, family members or other individuals not directly participating in the research) at a greater risk of harm (including physical, psychological, economic, or social harm) than was previously known or expected.

8.5.2 Unanticipated Problem Reporting

The investigator will report unanticipated problems (UPs) to the NIH Institutional Review Board (IRB) as per Policy 801.

8.5.3 NIH Intramural IRB Reporting of IND Safety Reports

Only IND Safety Reports that meet the definition of an unanticipated problem will need to be reported to the NIH Intramural IRB.

1 STATISTICAL CONSIDERATIONS

9.1 STATISTICAL HYPOTHESIS

Primary hypothesis:

Nutritional ketosis supplemented by MCT oil is feasible within a Parkinson Disease cohort as defined by an acceptable retention rate and outpatient adherence.

Primary outcome: Feasibility of nutritional ketosis(ketogenic diet with 80% lipid including MCT oil, 10-15% protein, 5-10% carbohydrate), in Parkinson Disease cohort defined as a composite outcome meeting all of the following criteria: recruitment target of 32 or as per interim power analysis defined in Section 9.4.6; retention rate > 80% at study end; adherence to ketogenic diet in the outpatient portion defined as mean carbohydrate energy intake <10%, and intervention is acceptable to all participants by Likert scale \geq 2/4 of likelihood of using this therapy in the future and effectiveness in symptom reduction, from all study participants at 3 weeks.

Secondary hypothesis:

Abbreviated Title: Tolerability and efficacy of ketogenic diet in Parkinson's Disease

Version Date: 04/19/2021

Nutritional induced ketosis (NK) increases mobility based on TUG score in a Parkinson Disease cohort at 7 days compared to usual diet (35% lipid, 10-15% protein, 50-55% carbohydrate). Secondary outcome: timed Up & Go test (TUG score) at study day 7 (fastest of three trials)

$H_0: \mu_1 = \mu_2$, where μ_1 and μ_2 are the population means for the NK diet group and usual diet group respectively vs. $H_1: \mu_1 \neq \mu_2$.

Exploratory hypotheses:

Hypothesis A: Nutritional ketosis improves PD symptomatology in cognition (improved attention, recall, and executive function, and motor function akinesia and tremor within six days, as assessed by: Stroop word-color interference latency (executive function), n-back recall task (attention and working memory), simple reaction time (akinesia); fingertap speed and rhythm MN and PQ keyboard tasks (fine motor), and autonomic function (heart rate variability at rest and with deep breathing / Valsalva Maneuver tests)

Hypothesis B: The mechanism of symptomatic reduction of NK in PD is both augmented mitochondrial metabolism (direct, rapid) and augmented neurotransmitter and growth factor synthesis (indirect, delayed), especially GABA and dopamine, as assessed by resting state EEG spectral power, phase coherence, and M1 waveform normalization. Accordingly, effect sizes for exploratory outcomes will be greater at 3 weeks than 7 days.

Exploratory outcomes daily (days 1-7), week 3

ON/OFF time (daily subjective worksheets), keto-induction symptoms (daily worksheets or self-report), UPDRS-III motor score, MN and PQ keyboard tasks, simple and complex reaction time, 9-hole pegboard test, 3-back recall, Stroop word color interference and latency, tremor amplitude, heart rate variability heart rate variability (SDNN, pNN50, rMSSD, power spectral analysis).

Exploratory outcomes day 1, 7, and week 3:

Valsalva Maneuver and deep breathing cardiovagal tests), plasma BDNF, Geriatric Depression Scale (GDS), EEG sensorimotor spectral power (Hall et al, 2014) and M1 waveform peak:trough asymmetry (Voytek and Cole, 2017).

As an effect of the intervention at three weeks, there is expected to be decrease in EEG beta power on the more affected hemisphere clinically, relating to attenuation of pathologic pallidal GABA efferents to a greater extent than at 7 days or baseline. Similar trends are anticipated for attenuation of M1 waveform asymmetry, reduction in UPDRS total and subtotal scores, decreased latencies and total time of motor task performance tests, improved accuracy and speed of cognitive tasks, and increase in plasma BDNF and heart rate variability measures. The effect on depression symptoms is unclear but reduction is proposed.

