- Outcomes:** The primary outcome is feasibility, as determined by a composite outcome of recruitment and retention, acceptability and adherence, including full recruitment to study target of 32 participants; completion rate >80% in both inpatient 1-week and outpatient 2-week segments; adherence in the outpatient segment of estimated low carbohydrate diet <10% mean total

Abbreviated Title: Feasibility and efficacy of ketogenic diet in Parkinson's Disease

Version Date: 04/19/2021

daily energy defined as net carbs); and acceptability defined via exit survey (week 3) 4-point Likert efficacy and likelihood scales on how effective ketogenic diet appears on symptoms and how likely ketogenic diet, with or without MCT oil, participants estimate they will continue the diet on at least an intermittent basis in the future.

The secondary outcome is Timed up & go (TUG) mean difference between groups at the end of admission (day 7).

Exploratory outcomes include both group comparisons (mean difference) at day 7 and repeated measures days 1-7 between MCT-KD and SAD groups (in most but not all outcomes; refer to section 1.3 Schedule of Activities for details) and at week 3, when both groups combine to a single ketogenic diet group, and within-group pre vs. post intervention comparisons at 1 & 3 weeks for both groups separately (SAD at 0 & 2 weeks of ketogenic diet vs. MCT-KD group at 1 & 3 weeks, respectively) and all participants, in the following: Stroop word-color interference latency (executive function), n-back recall task (attention and working memory), finger tap speed and rhythm (MN and PQ keyboard tasks), accelerometry amplitude for tremor analysis; 9-hole pegboard test (9-HPT) (daily), heart rate variability HF power, total power (resting, daily), cardiovagal testing via deep breathing and Valsalva Maneuver (pre vs. post), mean subjective on vs. off time (pre vs. post), non-motor severity score (NMSS) pre vs. post, keto-induction symptoms, UPDRS (pre vs. post), EEG spectral power by frequency and connectivity analysis (day 1 vs. day 7 vs. week 3), Geriatric Depression Scale (GDS, pre vs. post)

Study Population:

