Idiopathic Parkinson's Disease of moderate severity, Hoehn & Yahr Stage 2-4, age >50, usual (carbohydrate predominant) diet at baseline. A total of 32 PD patients will be recruited predominantly from the Parkinson's Clinic at NIH and local sites given necessity of three visits to facilitate randomization and baseline data acquisition. Recruitment will continue as per power analysis for Timed Up & Go (TUG).

Phase:	1
Description of Sites/Facilities	Enrollment will occur at Screening Visit, NIH Clinical Center Outpatient Clinic 5 (OP5). Admission will occur at NIH Clinical Center Metabolic Unit, 7SW.
Enrolling Participants:	Unit, 7SW.
Description of Study Intervention:	The study intervention is randomization to MCT-KD (ketogenic diet with 80% energy from lipids including Liquigen® (KetoCal) comprising 25% of the daily lipid energy divided twice daily or typical, standard American diet (SAD) x 6 days, followed by 2 weeks ketogenic diet in both groups at home. The proposed diets are isocaloric and have the same ratio of protein (10-15% daily energy) with similar mealtime boluses to limit differences in L-DOPA absorption. Daily activity and exercise plans will be individualized upon admission including use of stationary bike, aiming to maintain baseline levels. Diet with MCT oil will begin on hospital day 2

[figure not shown]
Abbreviated Title: Feasibility and efficacy of ketogenic diet in Parkinson’s Disease

Version Date: 04/19/2021

and be provided to both groups at outpatient day 1 Both diets will be double-blinded (combination of shakes and similar appearing snacks). MCT-KD will feature reduced carbohydrate intake of 5-10% daily energy requirement calculated in the Metabolic Unit. Safety monitoring will be performed by IMM.

Study Duration: 9 months
Participant Duration: 3 weeks

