3. OBJECTIVES AND ENDPOINTS

OBJECTIVES	OUTCOME MEASURES	JUSTIFICATION FOR ENDPOINTS
Primary		
Feasibility of MCT-KD x three weeks	Composite outcome (all of the following measures must be met):	MCT-KD has never been studied in PD population (expected to

Abbreviated Title: Tolerability and efficacy of ketogenic diet in Parkinson's Disease**Version Date:** 04/19/2021

	
1) Recruitment reaches target of 32 participants or as per pre-set interim analysis
 
2) Study retention rate >80% of all participants at 3 weeks
 
3) Adherence ($\leq 10\%$ mean daily energy from net carb over 2 weeks MCT-KD outpatient, assessed by 2x/week unscheduled phone calls by CC Nutrition staff)
 
4) Acceptability – Likert scale ≥ 2 (at least somewhat likely to use diet in future and at least somewhat effective in improving PD symptoms) at end of study (week 3)
	augment ketosis) and feasibility has not been established.
Secondary		
Timed Up & Go (TUG) time, mean difference between groups on study day 7	Mobility on the Timed Up and Go (TUG) test, daily (fastest of three trials per session) units: seconds Range: 8-18s	TUG time is generally regarded as an index of fall risk – estimated 20% risk reduction with 4s faster time (Nocera et al, 2013)
Tertiary/Exploratory		

Nutritional ketosis (NK) improves PD symptomatology at three weeks in the following: in cognition (improved attention, recall, and executive function), and motor function (reduced akinesia and tremor). A low fat (standard American) diet (SAD) does not.
 
NK reduces non-motor symptoms, subjective motor fluctuations and daily off time within the immediate keto-induction period, while SAD does not (mean difference at 1
	
Stroop word-color interference latency (unit: ms, range: 110-135 ms), 0,1,2,3 back recall task (unit i: % error of missing true n-back letter presented; range i: 0-back 0-10%, 1-back 4-20%, 2-back 15-30%, 3-back 20-32%; unit ii reaction time (RT) ms, range ii 0-back 500-740 ms; 1-back 600-980 ms; 2-back 700-1200 ms; 3-back 700-1200 ms); fingertap speed and rhythm (MN and PQ keyboard tasks; units MN and PQ keystroke speed, in keys/s; range MN
	
All of these tests have been shown to be impaired in PD cohorts and are at least semi-quantitative and amenable to serially repeated measures with good test-retest reliability
 
Scalp EEG is non-invasive, easy to perform in the setting of intervention, and as

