Of methodological importance, a learning effect is expected in repeated tests, more so in the proposed tests involving preparation and decision such as Stroop word-color interference, TUG, and 3-back recall. However, the underlying assumption of learning effect is that it is expected to be equivalent in both randomized study conditions, and moreover is of study interest for between-group effect though not directly measured. The tests were selected as ones with established reliability of repeated testing, which is operationally validated for simple motor tasks - simple reaction time (18 trials, Hamsher 1977), 9-hole pegboard test, MN-PQ keyboard tapping speed, and TUG. On the other hand, there is greater potential learning bias in cognitive tasks, particularly visuo-verbal 3-back working memory task (Soveri et al 2018) where test-retest reliability has been reported as moderate, whereas simple reaction time reliability is much higher. Nonetheless, it is the aim to adjust for learning effect by randomization between the groups stratified by age. Learning effect could account for some of the difference in performance between the groups particularly in cognitive tasks. The goal is to capture which types of testing improve, whether ones more (n-back test, Stroop word-color interference) or less (reaction time, tapping speed, TUG) subject to learning effect, to infer appropriately whether or not learning effect may be considered to be operative in any difference between the groups.

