The combination of inpatient and outpatient parts of the study involves some degree of discontinuity of the diet, at least in terms of monitoring but also in the diet itself. The latter difference is due to the desire to maintain double-blinding in the inpatient part of the study to minimize placebo effect, while also wanting to assess feasibility of a diet that is thought to be better tolerated than traditional, strict 4:1 (4 grams lipid to 1 gram carb + protein) ketogenic diets. The inpatient diet is predominantly liquid via blended nutrients to facilitate the blinding, but this is not practical to recommend for long-term outpatient therapy. Furthermore, while there is possibility to maintain a control group in the outpatient part of the study, it is felt preferable to prescribe ketogenic diet to all participants outpatient for a few reasons. First, study power will be increased for the key portion of the study: feasibility of MCT-KD in the home. Second, regardless of inpatient randomization group, all participants will have opportunity to try the

Abbreviated Title: Tolerability and efficacy of ketogenic diet in Parkinson's Disease

Version Date: 04/19/2021

ketogenic diet as possible therapy, which should improve study recruitment and limit possible “nocebo” effect that an outpatient control group might otherwise be subject to.

Herein is proposed an inpatient pilot study of MCT ketogenic diet (MCT-KD) compared to standard American diet (SAD) in randomized, double-blind participant groups followed by outpatient study of a similar ketogenic diet with education and meal preparation guidelines, monitored for the inpatient portion with fingerstick beta-OHB levels, continuous glucose monitoring, and respiratory quotient and outpatient via online meal planning app, Diet tracking, correlating with motor physiology, cognitive inhibition and short-term recall, and EEG characteristics to establish which, if any, aspects of known PD test impairments may be modulated by ketogenic intervention in relation to suspected or likely metabolic pathways, to inform subsequent study into symptomatic benefit and/or disease modification.

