9.4.3 Analysis of the Exploratory Outcomes

ANCOVA will be also used to examine the diet effect on the other exploratory outcomes, where each outcome measure over time will be used as a dependent variable with age and the outcome at day 1 as covariates.

Longitudinal analysis methods, such as repeated measures ANCOVA, random coefficient model or mixed model, will be used to examine the change in the exploratory outcomes over the six days. Within-subject

Abbreviated Title: Tolerability and efficacy of ketogenic diet in Parkinson's Disease

Version Date: 04/19/2021

(mixed model) and across-subject (spearman or Pearson) correlation analysis will be applied to evaluate the relationship between outcome variables.

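### No participant is on the standard diet after day 7, so the three-week contrast with that diet cannot be tested and Hypothesis B has no sound test as written

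*Combined protocol and SAP*

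**What the plan says.** **Claims.** The exploratory objective in section 3 reads "Nutritional ketosis (NK) improves PD symptomatology at three weeks in the following", lists cognitive and motor domains, and then says of the comparator: "A low fat (standard American) diet (SAD) does not". Section 9.1, Hypothesis B, proposes a rapid metabolic mechanism and a slower neurotransmitter and growth-factor mechanism, and concludes: "Accordingly, effect sizes for exploratory outcomes will be greater at 3 weeks than 7 days". The text that follows extends the same expectation to motor and cognitive tests, BDNF and heart rate variability (HRV).

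**Design.** The synopsis (section 1.1) gives the inpatient week, "followed by 2 weeks ketogenic diet in both groups at home", and describes comparisons "at week 3, when both groups combine to a single ketogenic diet group". Section 4.2 considers an outpatient control and rejects it: "it is felt preferable to prescribe ketogenic diet to all participants outpatient for a few reasons".

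**Practice.** Section 4.2 expects learning on repeated tests and answers it in this way: "the underlying assumption of learning effect is that it is expected to be equivalent in both randomized study conditions".

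**Analysis.** Section 9.4.3 says "ANCOVA will be also used to examine the diet effect on the other exploratory outcomes" but does not say which contrast applies at week 3. The repeated-measures TUG model in section 9.4.2 covers day 1, day 7 and week 3, yet names its between-subject factor as ketogenic against standard diet throughout. The synopsis also plans pre-post comparisons at 1 and 3 weeks, in each arm and in all participants.

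**The concern.** A claim that one diet helps at three weeks and another does not needs people on both diets at three weeks. Here there are none on the standard diet. The plan's defence against practice, that it is equal in the two randomised conditions, protects the day-7 arm comparison but not a within-group change at week 3. By then each daily test has been taken in seven earlier sessions (section 1.3).

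What is at stake is interpretation. A week-3 gain could be read as support for the delayed mechanism in Hypothesis B when the design cannot separate it from practice, time, return home, or expectation on a diet that participants now know they are eating. Conversely, a shrinking arm difference at week 3 could be read as a fading effect when the comparator has simply started the same diet.

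**Working it through.** **1. Exposure by visit** (sections 1.1 and 6.1.1)

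| Visit | MCT-KD arm | SAD arm | Arms differ by |
|---|---|---|---|
| Day 1 | 0 days | 0 days | nothing |
| Day 7 | 6 days | 0 days | diet |
| Week 3 | 6 + 14 = 20 days | 14 days | 6 days of exposure |

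**2. The plan's own figure.** The point has no stated figure of its own. The only sizing in the plan is for day-7 TUG (section 9.2): difference 4.5 s, SD 4 s, two-sided alpha 0.0492, 80% power. With d = 4.5/4 = 1.125 and 14 per group, the noncentrality is 1.125 × √(14/2) = 2.98 on 26 df, which gives 81.5% power; 13 per group gives 78.4%. So 14 per group is right, and 28/0.9 = 31.1 leads to 32. I use 14 per arm (28 completers) below.

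**3. Hypothesis B read between arms.** Let E(t) be the diet effect after t weeks, with practice equal in both arms. The arm difference is E(1) at day 7 and E(3) − E(2) at week 3.
- Constant effect of 0.5 SD: 0.50 at day 7, 0.5 − 0.5 = 0.00 at week 3.
- Growing effect (0.5, 0.8, 0.9 SD at 1, 2, 3 weeks): 0.50 at day 7, 0.9 − 0.8 = 0.10 at week 3.

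In simulation (20,000 trials per scenario), the week-3 difference exceeded the day-7 difference in about 4% and 8% of trials. On this reading Hypothesis B would usually look false even though the diet works.

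**4. Hypothesis B read within group, pooled, with no diet effect.** Assumptions not in the documents: correlation between visits 0.7; practice gains of 0.3-0.6 SD. SD of change = √(2 × (1 − 0.7)) = 0.775 SD. SE = 0.775/√28 = 0.146 SD. Gains of 0.3, 0.5 and 0.6 SD therefore give expected t of 2.05, 3.42 and 4.10.

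| Practice gain, day 7 → week 3 | Pooled week-3 gain significant | Week-3 gain exceeds day-7 gain | That excess significant |
|---|---|---|---|
| 0.3 → 0.5 | 91% | 92% | 26% |
| 0.5 → 0.6 | 98% | 76% | 10% |
| 0.5 → 0.5 | 91% | 50% | 2.5% |
| 0.5 → 0.3 | 51% | 9% | 0% |
| none | 2.4% | 50% | 2.6% |

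Between-arm tests at day 7 and at week 3 kept about 5% false positives in every row. So practice readily mimics a week-3 improvement. It produces week 3 above day 7 reliably only if it keeps rising across the two weeks at home.

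**5. A controlled week-3 contrast already in the data.** Take the day-7-to-week-3 change in the SAD arm, which starts the diet, minus that in the MCT-KD arm, which continues it. Equal practice cancels, leaving E(2) − [E(3) − E(1)].
- Constant effect of 0.5 SD: 0.5 − 0 = 0.50.
- Growing effect as above: 0.8 − 0.4 = 0.40, against a true two-week effect of 0.80.

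SE = 0.775 × √(2/14) = 0.293 SD. A day-7 change contrast of 0.5 SD has the same SE and was significant in about 38% of simulated trials, so power here is of that order.

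**The case against.** The merger of the arms is deliberate and disclosed. Section 4.2 gives reasons: more information on home feasibility, easier recruitment, less nocebo effect. The synopsis already sets SAD at 0 and 2 weeks of diet against MCT-KD at 1 and 3 weeks. Hypothesis A already places the cognitive and motor claim within six days, inside the randomised window. Raters stay blinded to allocation until measurement ends (section 6.3). All this concerns exploratory outcomes in a phase 1 feasibility pilot. These points stand. They limit the stakes, but they do not supply a standard-diet comparator at week 3, and blinding to allocation cannot mask diet once everyone is on the same one.

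A reader might go further and infer that practice alone would confirm both claims. The documents do not support that.
- Practice cannot confirm that the standard diet gives no benefit at three weeks, because no such data exist. At day 7 it would improve the standard-diet arm too.
- Practice gives week 3 above day 7 reliably only if gains keep rising. With a plateau it is a coin toss, and with decay it is rare.
- Hypothesis B names resting EEG measures, and the following text adds BDNF and HRV. These are not skill tests. For them the threat is the missing control (time, expectation, open diet).

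A reader might also infer that Hypothesis B will be tested by setting a controlled day-7 arm difference against an uncontrolled week-3 change. No section plans that comparison: section 9.1 leaves the effect size undefined, and the synopsis plans pre-post change at both 1 and 3 weeks. Likewise, a large t for pooled week-3 change tests that change against zero, not week 3 against day 7.

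**Conclusion.** The concern holds in a limited form. The three-week contrast with the standard diet in section 3 cannot be tested, and the section 9.4.2 factor is mislabelled at week 3. These two conclusions follow from the text and need no assumption.

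Hypothesis B lacks a defined effect size, and neither like-for-like reading is a sound test. Between arms, a real constant effect goes to zero at week 3. Within group, a pooled week-3 gain would be significant in about 51-98% of trials with no diet effect. That range rests on the assumed gains of 0.3-0.6 SD, correlation of 0.7 and 28 completers. It applies to the repeated performance tests only, and section 4.2 is itself inconsistent on whether TUG is among the more or the less learning-prone.

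The primary feasibility outcome and the day-7 TUG comparison are unaffected. The change is worth making because it costs little and prevents an over-read mechanistic claim.

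**What to change.** 1. In section 3, restrict diet-versus-standard claims to the randomised day-7 comparison, in line with Hypothesis A, and delete the three-week statement about the standard diet.
2. For outcomes measured on day 1, day 7 and week 3, prespecify the arm difference in day-7-to-week-3 change (SAD arm starting minus MCT-KD arm continuing) as the controlled week-3 contrast. In section 9.4.2, relabel the factor at week 3 as early versus delayed start.
3. Define Hypothesis B's effect size on the same scale at both times. Report every other week-3 change as uncontrolled pre-post, including outcomes that section 1.3 schedules only at screening and week 3, such as NMSS and PDQ-39.

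The cost is wording in the objectives and analysis sections, with no new visits or data. There are downsides. Week-3 claims become weaker. The delayed-start contrast has modest power and understates the effect if the MCT-KD arm is still improving. Expectation may also differ between starters and continuers, since the discharge debriefing in section 8.2.4.2 includes education on the diet given. The last two should be stated as limitations.
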